Next, participants will be instructed to ingest one of the color-coded vials. Half the participants (those assigned odd ID codes) will be assigned to ingest the blue vial containing 20mg CBG first and the other half (those assigned even ID codes) will be assigned to ingest the yellow vial containing 20mg placebo first. The CBG tincture is composed of 10 mg/ml CBG, 0.89 mg/ml CBGA, beta-caryophyllene 0.35 mg/ml (0.51 mg/ml total terpenoids). It is derived from a CBG-dominant hemp plant containing less than the 0.3% THC limit imposed in the U.S. Agricultural Improvement Act of 2018. Single 3ml amber vials will be prepared with this material containing 2ml each representing a dose of 20mg of CBG. Chartreuse liqueur (55% ethanol by volume) prepared by Les Peres Chartreux, France 1ml, diluted with 1ml filtered water will be employed as the placebo as it provided a reasonable match for the green color and herbal/ethanol taste of the CBG tincture. Opaque vials will be labeled with color coded tabs (Blue = CBG, Yellow = Placebo) in double-blind fashion and mailed directly to study participants. To dilute the taste, participants will be instructed to mix the contents of the vial in a small glass of water prior to ingestion.

After observing the participant orally ingest the product, the RA will instruct them to complete an online survey that contains measures of their demographic characteristics; anxiety, depression, and stress levels; as well as their cannabis and CBG use patterns. Specifically, participants will be asked to provide information pertaining to their gender, age, ethnicity, education, personal income, work status, and marital status. They will also complete the Daily Sessions, Frequency, Age of Onset, & Quantity of Cannabis Use Inventory (DFAQ-CU) which is a 41-item inventory, with 24 core items that assess frequency, age of onset, and quantity of cannabis flower, quantity of cannabis concentrates, and quantity of edibles typically used [13]. The remaining items measure other aspects of cannabis use not commonly measured by other cannabis use scales (e.g., forms of cannabis; methods of administration; use for medical, recreational, or combined purposes). The

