One-week after the first testing session, participants will complete the second testing session. This session will be identical to the first testing session except those participants who ingested the blue vial containing CBG in the first session, will ingest the yellow vial containing placebo in the second session. Those who ingested the yellow vial containing placebo in the first session, will ingest the

blue vial containing CBG in the second session. Neither the participant nor the RA will know which color code corresponds to CBG and placebo.

Figure 1. Overview of Procedure for Each Testing Session

Safety Considerations

Risks of physical harm, discomfort, and psychological distress will be minimized by only recruiting individuals who have experience using cannabis-based products (have used these products at least 10 times) and by informing participants that they can skip questions they are not comfortable answering and cease tests they are not comfortable continuing. Our prior survey study on CBG indicates that CBG does not cause serious adverse reactions with only a minority of participants indicating they experience minor side effects (dry eyes, dry mouth, increase appetite, increased heart rate etc.). Nevertheless, participants who experience psychological distress will be provided with information about crisis lines and counseling services. If participants report any serious side effects from the CBG we will submit an adverse event report to the IRB and will cease further testing until guidance is provided from the IRB.

Follow-up

There are no plans to follow-up on participants unless they experience an adverse event.

Data Management and Statistical Analyses

Data Management: Data will be stored in a locked private office and on password protected encrypted computers. Prescreening data and survey data will be stored on Qualtrics and then downloaded onto a password protected encrypted computer. The Master list (linking ID codes to individual participants) will be stored on the PI's password protected encrypted WSU owned computer. The RA will enter the data into Excel on a password protected computer and data entry will be checked by an independent RA and/or the PI.

Power: Results of an a priori power analysis using G-Power indicate that a sample size of 34 will be required to achieve power of .80 to detect medium-sized effects (i.e., $d = 0.50$), with alpha set at .05.

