Data Analysis Plan: Pairwise deletion will be used to handle the small amount of missing data anticipated. Alpha will be set to .05 and effect sizes of 0.01 will be interpreted as small, 0.06 will be considered medium, and 0.14 and above will be considered large. Data will be analyzed using IBM SPSS v.27.

Percentages, means, and standard deviations will be used to determine the demographic characteristics and cannabis use patterns of the sample. Mean DASS subscale scores, mean subjective state (mood, anxiety, stress) ratings, mean STAI state and trait anxiety scores, and mean

subjective drug effect ratings will be computed at baseline (T0) for each condition.

Change scores will be created by subtracting baseline (T0) scores from T1, T2, and T3 scores for the subjective state ratings (anxiety, stress, mood), STAI state anxiety scores, and subjective drug effect ratings (dry eyes, dry mouth, sleepiness, appetite, heart palpitations/racing heart).

Primary Outcomes: To assess the primary outcome (determine the effects of CBG vs. placebo on anxiety, stress, and mood) a series of 2 x 3 repeated-measures ANCOVAs will be conducted with condition (CBG, placebo), and time (T1, T2, T3) as within-subjects factors, order of drug administration as a covariate, and changes (difference from T0 to T1, T2, T3) in ratings of anxiety, stress, and mood as separate dependent variables.

Secondary Outcomes: To assess the effects of CBG on subjective drug effect ratings (dry eyes, dry mouth, sleepiness, appetite, heart palpitations/racing heart) a series of 2 x 3 repeated-measures ANCOVAs will be conducted with condition (CBG, placebo), and time (T1, T2, T3) as within-subjects factors, order of drug administration as a covariate, and changes (difference from T0 to T1, T2, T3) in these subjective drug effect ratings as the dependent variables.

To determine the effects of CBG vs. placebo on intoxication, drug effect, and drug liking ratings a series of 2 x 3 repeated-measures ANCOVAs will be conducted with condition (CBG, placebo), and time (T1, T2, T3) as within-subjects factors, order of drug administration as a covariate, and ratings of each indicator of drug effects as the dependent variables.

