To examine the acute effects of CBG on verbal memory, a 2 x 5 repeated-measures analysis of covariance (ANCOVA) will be conducted with condition (CBG, placebo), and CVLT-II trial (Trial 1, Trial 2, Trial 3, Trial 1B, Short-Delay) as within-subjects factors, order of drug administration as a covariate, and number of words correctly recalled as dependent variable.

Finally, to assess the effects of CBG vs. placebo on impairment, a one-way repeated measures ANCOVAs will be conducted to compare DRUID scores at baseline, in the CBG condition, and in the placebo condition, while controlling for order.

Expected Outcomes

CBG is increasing in popularity, with many individuals claiming this non-intoxicating legal substance has medicinal properties and effectively reduces anxiety, depression, pain, and symptoms of other medical conditions. While a small body of pre-clinical rodent studies support these claims currently no objective human research on the potentially beneficial or detrimental effects of CBG exists. As such, this will be the first objective examination of the potentially beneficial and detrimental effects of CBG on humans. Results will help to inform current and potentially future CBG users on its potential risks and benefits.

Dissemination of Results

Results will be disseminated at scientific conferences (e.g., International Cannabinoid Research Society, Gordon Research Conference) and in a scientific journal (<https://www.nature.com/articles/s41598-024-66879-0>). A press release will be issued by the PI's university following publication. [name] will be first author, [name] will be second author, [name] will be third author, and [name] will be last author.

Duration of the Project

Recruitment, testing, data entry, data analysis, and preparation of the manuscript are anticipated to require 2 years.

Problems Anticipated

There are no anticipated problems.

Project Management

[name] will train research assistants, oversee data collection, check the data for data entry errors, analyze the data, and prepare the manuscript.

[name] will advertise the study, helped collect and enter data, helped interpret the results, and help prepare the manuscript.

[name] and [name] assisted [name] in designing the study and will help prepare the manuscript.

Ethics

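### Order is entered as a covariate with no stated coding, so the condition test is the order-averaged CBG effect only if order happens to be centred or symmetrically coded

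*Combined protocol and SAP*

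**What the plan says.** Under Data Analysis Plan, Primary Outcomes, the plan specifies "a series of 2 x 3 repeated-measures ANCOVAs will be conducted with condition (CBG, placebo), and time (T1, T2, T3) as within-subjects factors". It then adds "order of drug administration as a covariate, and changes (difference from T0 to T1, T2, T3) in ratings of anxiety, stress, and mood", with one model per outcome. Side effects and drug-effect ratings get the same model, and CVLT-II gets a 2 x 5 version with "order of drug administration as a covariate, and number of words correctly recalled as dependent variable". The DRUID analysis is a one-way ANCOVA that also controls for order. The software is fixed: "Data will be analyzed using IBM SPSS v.27".

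Order has two levels, set by ID code: "Half the participants (those assigned odd ID codes) will be assigned to ingest the blue vial containing 20mg CBG first", and the rest take placebo first. The plan does not say what numbers stand for the two orders, whether they are centred, or whether order could be a between-subjects factor. It names no period term and no condition x order test.

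Two further passages bear on the point. For the subjective state and side-effect ratings, "Change scores will be created by subtracting baseline (T0) scores from T1, T2, and T3 scores". On the second session, Testing Sessions says: "This session will be identical to the first testing session except" for the vial taken.

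The Results section reports the condition test for anxiety as F(1, 32) = 4.88, p = .034, and reads it as an overall difference between CBG and placebo.

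**The concern.** Order is a design factor with two levels, not a measured covariate. A repeated-measures GLM uses a covariate at the values the analyst typed in, and its within-subject main effects are evaluated where the covariate equals zero. If zero is not midway between the two orders, the condition test is no longer the average CBG effect.

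In a two-period cross-over, the difference between orders in the CBG-minus-placebo contrast carries the period effect. Counterbalancing is there to cancel that effect, and an uncentred order code puts it back into the condition test. The time and condition x time tests, and the secondary models, are evaluated at order = 0 in the same way. Two things are at stake: the type I error of the condition tests if a period effect exists, and the planned power whether or not one exists.

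**Working it through.** **Inputs.** From the documents: N = 34, d = 0.50, alpha .05, power .80 (Power); equal allocation to two orders (Testing Sessions); F(1, 32) = 4.88 for anxiety (Results). Assumed: 17 analysed per order, a two-sided test, and the period effects used below, because the documents give none.

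**The plan's own figure.** A two-sided paired t-test with d = 0.50 and N = 34 (33 df) has power 0.808, so the stated sample size reproduces.

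**What the condition test estimates.** Let D be one person's CBG-minus-placebo difference, averaged over time points, with SD 1 within order. Let tau be the CBG effect and pi the session-2-minus-session-1 effect, in SDs of D. Then mean D is tau - pi for CBG-first and tau + pi for placebo-first. With order as a numeric covariate, D = b0 + b1 x order, and the condition F tests b0 = 0 on 34 - 2 = 32 df.

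- -1/+1, or mean-centred with equal groups: b0 = tau. Variance 1/34, SE 0.171.
- 0/1: b0 is the mean of the group coded 0, which is tau - pi or tau + pi. Variance 1/17, SE 0.243.
- 1/2: b0 = 2 x (mean of group 1) - (mean of group 2), which is tau - 3pi or tau + 3pi. Variance (4 + 1)/17 = 10/34, SE 0.542. This extrapolates outside both groups.

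**Power at d = 0.50 with pi = 0.** The noncentrality is 0.25 divided by the variance, on F(1, 32):

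| Coding | Noncentrality | Power |
|---|---|---|
| Factor, centred or -1/+1 | 8.5 | 0.807 |
| 0/1 | 4.25 | 0.516 |
| 1/2 | 0.85 | 0.145 |

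**Type I error with tau = 0.** The noncentrality is pi² x 17 for 0/1 and (3pi)² x 17/5 for 1/2:

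| Assumed pi | Factor or centred | 0/1 | 1/2 |
|---|---|---|---|
| 0 | 5% | 5% | 5% |
| 0.2 | 5% | 12.6% | 18.9% |
| 0.3 | 5% | 22.4% | 36.3% |

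**Which coding was used.** The error df cannot show this: 32 df follow from one order term in 34 people under any coding, and equally from a between-subjects factor. F = 4.88 on (1, 32) df gives p = .034 and eta-squared .132, as reported. That confirms the arithmetic but not the model.

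**What the anxiety result could mean, if the code was 0/1.** The tested quantity would be √4.88 x 0.2425 = 0.536 SD. With pi = 0, the averaged effect would give t = 0.536/0.1715 = 3.12, p = .004. If a period effect of 0.2 SD had added to it, t = (0.536 - 0.2)/0.1715 = 1.96, p = .059. The reported p could therefore overstate or understate the evidence.

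**The case against.** The strongest reply is that the leak is not automatic. The plan calls order a covariate and stops there. A covariate has no default code, and an analyst who centred it, used -1/+1 with equal groups, or in fact entered order as a factor would have tested the averaged effect with power 0.81. This stands. A reader might infer that the reported anxiety result is contaminated, or that the planned power was lost. The documents do not support either inference, because they give neither the coding nor the means by order.

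Second, the primary outcomes are changes from the same session's T0. Any shift common to T0 and the later ratings cancels, including general unease about a session whose content is already known. This also stands. For anxiety, stress and mood, only a period effect on the change itself matters, such as habituation to the repeated stress test. The protection does not extend to CVLT-II or to the intoxication, drug-effect and liking ratings, which are analysed without subtracting T0 and are exposed to any session shift. The alternate CVLT-II word lists are meant to limit practice effects, so a period effect there is possible but not established.

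Third, the period effects of 0.2 and 0.3 SD are assumptions, and with no period effect type I error is 5% under every coding. True, but the power loss under 0/1 or 1/2 needs no period effect.

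Fourth, the 17-per-order figures do not carry over exactly to CVLT-II. Its 30 error df imply about 30 + 2 = 32 people, with the split by order not given.

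**Conclusion.** The concern holds as a specification gap with conditional consequences. As written, the plan lets an analyst enter an uncentred order code and test something other than the average CBG effect, and a reader cannot tell whether that happened. If the code was 0/1 or 1/2, the condition test estimates the CBG effect plus or minus one or three times the period effect. Power at d = 0.50 is then 0.52 or 0.15 instead of 0.81. With an assumed period effect of 0.2 to 0.3 SD, type I error is about 13-22% or 19-36%. If order was centred or coded -1/+1 in equal groups, or entered as a factor, there is no such bias and no such loss.

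The figures rest on 17 analysed people per order and a two-sided test. The direction and size of any bias in the reported results are unknown. The point deserves correction because it touches every primary condition test and the remedy is nearly free.

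**What to change.** In every model, replace order as a covariate with order as a between-subjects factor. State that the condition effect is the equally weighted average over the two orders, and report condition x order as the period effect. The error df stay at 32 and power at 0.81, whatever numbers label the orders.

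For the results already given, state the coding that was used. If order was neither a factor nor coded so that zero is the midpoint of the two orders, re-run the anxiety, stress, mood, CVLT-II and DRUID tests. For CVLT-II, give the number analysed in each order; mean-centring with unequal groups would weight the orders by size, whereas the factor version need not.

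A mixed model is a sound alternative only if it has a participant-by-condition random term and a period x time term. With a random participant effect alone, condition is tested on a pooled residual with 34 x 6 - 34 - 6 = 164 df (the second 6 being condition 1, time 2, condition x time 2 and period 1). In simulation, type I error was then about 13%, 22% and 31% when person-by-condition variance was 25%, 50% and 75% of within-person variance.

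The cost is an edit to the model wording throughout the analysis plan and a small reanalysis, with no new data.

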After completing three baseline trials of the DRUID app participants will schedule their testing sessions. The PI or RA will assign their ID code (sequentially) and will provide the participant with contact information of a CBG producer who will ship color-coded vials of hemp derived CBG and placebo directly to them. Finally, participants will be instructed to abstain from using any cannabis products including CBG for a minimum of 24 hours prior to their testing session.

Testing Sessions: Approximately one-week after the pre-testing Zoom session, participants will meet with a RA (blinded to the color-codes used for the drug and placebo) on Zoom for their first testing session. First, the RA will confirm that participant has abstained from use of cannabis or CBG for a minimum of 24 hours prior to the testing session. As depicted in Figure 1, participants will then provide baseline (T0) ratings of their subjective state (anxiety, stress, mood). Specifically, participants will rate their subjective levels of anxiety and stress using 0 (not at all) to 10 (extremely) visual analogue scales, and they will rate their subjective mood using a 0 (extremely negative) to 10 (extremely positive) visual analogue scale. They will also complete the state form of the State-Trait Anxiety Inventory, which assesses symptoms of anxiety participants are experiencing in the moment [12].

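### The primary analysis subtracts each session's T0 rating instead of estimating its slope: a valid test, but probably less precise than the data allow

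*Combined protocol and SAP*

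**What the plan says.** Under Data Analysis Plan, "Change scores will be created by subtracting baseline (T0) scores from T1, T2, and T3 scores for the subjective state ratings", and likewise for STAI state anxiety. Under Primary Outcomes, the 2 x 3 repeated-measures ANCOVAs (condition by time) take "changes (difference from T0 to T1, T2, T3) in ratings of anxiety, stress, and mood as separate dependent variables", with "order of drug administration as a covariate". No other covariate is named, so the label ANCOVA refers to order and not to baseline.

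T0 is a pre-dose measurement taken in every session. Under Testing Sessions, anxiety, stress and mood are rated before the vial is taken. Of the second visit the protocol says "This session will be identical to the first testing session except" for which vial is used. Each participant therefore has two T0 values, one per condition.

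The Results section agrees with this reading. The condition effects for anxiety, stress and mood are all F(1, 32), and 34 participants minus one for the mean and one for order leaves 32. No section plans a model with T0 as a covariate, even as a sensitivity analysis.

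**The concern.** Subtracting T0 is the same as adjusting for it with a coefficient set to 1 in advance. If the true coefficient is smaller, the change score carries surplus T0 noise into the CBG-placebo contrast, and a chance T0 difference between a participant's two sessions is over-corrected. Estimating the coefficient uses the same data and costs one error degree of freedom for the condition effect.

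What is at stake is precision, in a trial of 34 with no stated allowance for dropout. Two of the three primary condition effects lie near the 0.05 threshold: anxiety at p = .034 and mood at p = .081.

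**Working it through.** **Step 1: reproduce the plan's figure.** Under Power, a "sample size of 34 will be required to achieve power of .80 to detect medium-sized effects" (d = 0.50, alpha .05). Test family and sidedness are not stated. A two-sided paired t-test with standardised difference 0.50 needs N = 34 (power 0.808), so the figure reproduces. With order in the model (32 df), power is 0.807.

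**Step 2: general result.** For each participant take the CBG-minus-placebo difference at T0 and after dosing. Let r be the correlation of these two differences, scale the T0 difference to SD 1, and let k be the SD of the post-dose difference. The slope of post-dose on T0 is b = rk.

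- Variance of the change contrast: k² + 1 - 2rk
- Variance of the T0-adjusted contrast: k²(1 - r²)
- Excess from subtracting: (1 - b)²

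The excess is zero only when b = 1.

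**Step 3: one post-dose time point, equal variances (k = 1).** The variance ratio, adjusted over change, is (1 - r²) / [2(1 - r)] = (1 + r)/2. Power is at N = 34, taking d = 0.50 to be on the change score: 32 df for change, 31 df for adjusted.

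| r (assumed) | Change variance | Adjusted variance | Ratio | Power, change | Power, adjusted |
|---|---|---|---|---|---|
| 0.3 | 1.40 | 0.91 | 0.65 | 0.807 | 0.938 |
| 0.5 | 1.00 | 0.75 | 0.75 | 0.807 | 0.903 |
| 0.7 | 0.60 | 0.51 | 0.85 | 0.807 | 0.865 |

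Simulation with the slope estimated (20,000 runs per setting) gave power, change against adjusted, of 0.807 against 0.898 at r = 0.5, 0.813 against 0.836 at r = 0.8, and 0.804 against 0.802 at r = 0.95. Near r = 0.95 the lost degree of freedom cancels the gain. Under the null both methods rejected in 0.050 to 0.051 of runs.

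**Step 4: the planned condition main effect, averaged over T1-T3.** Assume equal variances and the same correlation r between any two time points. The mean of three post-dose differences has variance v = (1 + 2r)/3. The change variance is 1 + v - 2r and the adjusted variance is v - r².

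| r (assumed) | v | Change variance | Adjusted variance | Ratio | Power, adjusted |
|---|---|---|---|---|---|
| 0.3 | 0.533 | 0.933 | 0.443 | 0.475 | 0.984 |
| 0.5 | 0.667 | 0.667 | 0.417 | 0.625 | 0.946 |
| 0.7 | 0.800 | 0.400 | 0.310 | 0.775 | 0.894 |

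The gain is larger because averaging reduces post-dose noise but leaves the noise of the single T0 rating.

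**Step 5: unequal variances, one time point.** Ratings after a stress test may spread more widely than ratings at rest.

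- k = 1.5, r = 0.4: slope 0.60; 1.89 / 2.05 = 0.922, a cut of 8%.
- k = 1.5, r = 0.5: slope 0.75; 1.6875 / 1.75 = 0.964, a cut of 3.6% (power 0.820).
- k = 1.5, r = 0.6: slope 0.90; 1.44 / 1.45 = 0.993, a cut of 0.7%.
- k = 2, r = 0.5: slope 1; 3 / 3 = 1, no cut.

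**Step 6: which correlation matters.** r is between session differences, so stable personal levels cancel: r = (within-session correlation - between-session correlation) / (1 - between-session correlation). A within-session correlation of 0.7 with 0.5 between sessions gives 0.2 / 0.5 = 0.4. A high same-session correlation therefore does not by itself imply a high r.

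**The case against.** The strongest reply is that nothing is broken. The change-score contrast is unbiased, its type I error is correct, N = 34 is right, and change from a session baseline matches the stated hypotheses of decreased anxiety and stress and elevated mood. All of that stands; this is a point about efficiency.

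The second reply is that the size of the gain is unknown, and this stands too. A reader might infer, from a single 0-10 rating followed 20 to 60 minutes later by ratings that partly come after a stressor, that the T0 slope must be well below 1. The documents do not show it: they give no SD or correlation, and a wider post-dose spread pushes the slope up (Step 5). The power figures also depend on d = 0.50 referring to the change score, which the Power paragraph does not say.

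A reader might also infer that session-2 T0 is distorted because participants then expect the stress test. A mean shift of that kind is a period effect. It is balanced by the 1:1 allocation to the two orders and handled by the order term, so it does not support this point.

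Finally, a careless remedy could do harm. A mixed model with only a participant random intercept ignores variation between a participant's sessions. In null simulations at N = 34 it gave type I error of 0.11 to 0.17. Regressing the session difference on the T0 difference gave about 0.055. The remedy must therefore specify its covariance.

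**Conclusion.** The concern holds as a precision point. The primary models fix the T0 slope at 1 although a session-specific baseline is available, and they lose precision whenever the true slope is not close to 1. The variance reduction from estimating the slope runs from nil (slope 1), through about 4% (r = 0.5, post-dose SD 1.5 times the T0 SD), to 15-35% for one time point and about 22-52% for the T1-T3 average under equal variances with r from 0.7 down to 0.3. Every figure rests on assumed correlations and SDs.

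Two stronger readings go too far. A reader might infer that the reported anxiety or mood result is wrong or would change; the direction of any shift cannot be predicted without the data. A reader might also infer that this is the largest precision gain open to the trial at no cost; nothing in the documents permits that ranking.

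**What to change.** For anxiety, stress, mood and STAI state, add an analysis that estimates the T0 slope.

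- **Simplest form, condition main effect:** regress each participant's CBG-minus-placebo difference in mean T1-T3 rating on the CBG-minus-placebo T0 difference and centred order, and test the intercept. Leave the T0 difference uncentred, so that the intercept is the effect at equal T0 in the two sessions. Repeat at each time point as needed.
- **Mixed-model form:** model the T1-T3 ratings with condition, time, condition x time, period, sequence, the participant's mean T0 and the session's deviation from that mean. Include a random participant effect and a random session-within-participant effect (or an unstructured covariance), and use small-sample degrees of freedom. A participant intercept alone is not acceptable.

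A session-varying T0 cannot be entered as one ordinary between-subject covariate in the repeated-measures ANCOVA, so one of these forms is needed.

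Because the change-score p-values are already reported, keep those analyses as the prespecified ones and label the T0-adjusted model as a sensitivity analysis added afterwards. Specify it as primary only in a future plan. The cost is some syntax and one error degree of freedom for the condition effect; no new data are needed.
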